#### **5.7.5.2 Vaccine Reactogenicity**

All subjects will be observed for at least 60 minutes after each study vaccination to detect and treat any immediate AEs. Subjects will also complete study memory aids after each vaccination beginning with the day of vaccination and through 14 days after vaccination. Injection site reactions including bruising, redness, induration (hardness)/swelling, pain, and tenderness will be recorded on the study aids. Systemic reactions including fever, myalgia (body aches/muscular pains exclusive of the injection site), arthralgia (joint pains exclusive of the injection site), headache, nausea, and vomiting will also be recorded. Vaccine reactogenicity events are AEs that are known to occur with types of vaccine similar in composition to those being tested in this study.

Solicited and Unsolicited events post-vaccination will be summarized by frequency counts and percentages will be tabulated by severity to Vaccine Group and placebo using Safety Population. The number of subjects reporting a solicited adverse event will be summarized by day post vaccination for each vaccination and for all vaccinations combined both in tables and graphically in bar charts.

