- Any unresolved or continuing solicited or unsolicited Grade 3 adverse event. An unresolved or continuing Grade 1 or Grade 2 adverse event is permissible unless, in the opinion of the Principal Investigator or appropriate co-investigator, it would render study vaccination unsafe or interfere with the evaluation of responses.
- Grade 3 clinical safety laboratory value that does not decrease to Grade 2 or less prior to the second or third study vaccination or prior to planned CHHI. Any clinical safety laboratory parameter may be re-evaluated only once at the central (clinical) laboratory prior to the second or third study vaccination, or CHHI. If the clinical safety laboratory value decreases to Grade 2 or less, the subject may receive the second or third study vaccination, or CHHI. The second or third study vaccination, or the CHHI, should be scheduled to occur within the acceptable protocol-specified window for that visit. If outside this window, the Sponsor must first approve the study vaccination or CHHI and the documentation of approval should be filed in the subject's chart.
- Severe or sustained reaction or disability related to a preceding study vaccination.
- New onset of illness or condition that meets exclusion criteria.
- Subject no longer meets eligibility criteria.

- As deemed necessary by the Principal Investigator or appropriate co-investigator for noncompliance or other reasons.
- Subject refusal of further study vaccination.
- Subject withdrawal of consent.
- Subject lost to follow-up.
- Termination of the study.
- New information becomes available that makes further participation unsafe.

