## 5. STATISTICAL METHODOLOGY

### 5.1 General Considerations

The statistical analyses will be performed by Quartesian Clinical Research, using SAS Version 9.3 (or higher). All tables, figures and listings will be produced in landscape format. In general, all data will be listed by the subject and visit/time point where appropriate.

Data will be summarized by time-point where appropriate. The total number of subjects in the study group (N) under the stated population will be displayed in the header of summary tables.

Data will be summarized using descriptive statistics for continuous variables. Unless otherwise stated, descriptive statistics will include number of subjects, mean, standard deviation, minimum, median and maximum for all endpoints in case of  $n < 2$ , where n indicates the number of evaluable subjects at the particular time point, only n, mean, minimum and maximum will be displayed. The statistic "Missing" will also be evaluated by enumerating the number of missing entries/subjects, if any at that visit, and presented along with summary statistic. Display NC if any value is not computable.

Decimal Precision Convention: The minimum and maximum statistics will be presented to the same number of decimal places as the original data. The mean and median will be presented to one more decimal place than the original data, whereas the standard deviation will be presented to two more decimal places than the original data.

For categorical variables, counts and percentages will be used. The count [n] indicates the actual number of subjects with non-missing value at particular visit or actual number of subjects with that event or category, which should always be less than or equal to the total number of subjects in the respective study group [N]. Percentage will be obtained by:  $\% = (n/N) * 100$ .

Unless otherwise stated, all percentages will be expressed to one decimal place.

Also, the distributions for continuous variables will be examined for normality using Shapiro-Wilk tests. If any deviation in the normality assumption is judged, then the data will be analyzed using appropriate non-parametric tests.

The following conventions will be applied to analyses/data presentation:

All dates will be displayed in DDMMYY format.

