### **5.3 Analysis Populations**

**All Subjects:** All subjects will include the subjects who signed the informed consent form.

**Randomized Population:** The randomized population will include all subjects who were randomized to any one of the groups.

**Safety Population:** The safety population will include all randomized subjects who have received at least one dose of study vaccine. This population will be used to summarize safety variables and will summarize subjects as vaccinated.

**Immunization Population:** The immunization population will include all randomized subjects who received all three study vaccinations.

**Per Protocol Population:** The per protocol population will include all randomized subjects who received all three study vaccinations and CHHI and completed the study without any major protocol deviations or completed the study with a protocol deviation(s) having no significant impact according to Investigator's assessment.

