- Additionally, the proportion of subjects with at least one injection site AE and frequency of AEs grouped by SOC term will be compared by *Na-GST-1* vaccine formulation and placebo. The null hypotheses that the Adverse event type and number of adverse events is the same across all vaccination groups and placebo. 2-sided *p*-values will be obtained from the Fisher's exact test.

All AEs during the study will be summarized for the respective vaccination. A subject experiencing the same AE multiple times will be counted only once for that preferred term. Similarly, if a subject experience multiple AEs (preferred terms) within the same system organ class then that subject will be

counted only once for that system organ class. When summarizing by severity, only event with highest severity will be counted. All AEs will be listed in chronological order of the events occurred.

Individual subject listings containing all information pertaining to adverse events noted during the study will be presented by Vaccine Group, subject, verbatim and preferred terms, system organ class, start date, stop date, maximum severity, outcome, action taken and study vaccine relatedness.

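### SAP 5.7.5.2 summarizes reactogenicity dose by dose but names no dose-specific denominator, so percentages for doses 2 and 3 can be diluted by subjects who never received that dose

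*SAP*

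**What the plan says.** SAP 5.7.5.2 has two relevant sentences. The first says solicited and unsolicited events after vaccination will be "tabulated by severity to Vaccine Group and placebo using Safety Population". The second says the number of subjects with a solicited event will be "summarized by day post vaccination for each vaccination and for all vaccinations combined both in tables and graphically in bar charts".

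SAP 5.3 defines the population: "The safety population will include all randomized subjects who have received at least one dose of study vaccine". Nothing in it requires dose 2 or dose 3. SAP 5.7.5 assigns the safety analysis as a whole to the same population.

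SAP 5.1 gives the percentage rule, n divided by N times 100, and says of N: "The total number of subjects in the study group (N) under the stated population will be displayed in the header of summary tables". It adds that missing observations are included in the population size shown. No section defines an N for a particular dose. The Immunization Population in SAP 5.3 requires all three vaccinations and is not assigned to these tables.

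SAP 5.7.5.1 adds: "All AEs during the study will be summarized for the respective vaccination".

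Protocol 5.3.3 lists grounds on which dose 2 or 3 may not be given. They include "Severe or sustained reaction or disability related to a preceding study vaccination", a Grade 3 event that has not resolved, and the subject's refusal. Protocol 6.3 keeps subjects who miss a dose in safety follow-up, and protocol 5.3.1 does not replace anyone who leaves after the first vaccination.

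**The concern.** A subject who did not receive dose 2 or 3 cannot have a reaction to it. If that subject stays in N for that dose, the subject adds one to the denominator and nothing to the numerator. The printed percentage then mixes two things: how often the dose caused a reaction, and how often it was given.

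The mixing need not be equal across groups. If doses are withheld because of reactions, the group with more such reactions loses more from its printed rate at the next dose. A formulation could look closer to saline than it is among those dosed, or milder than another formulation that was fully dosed. Dilution confined to doses 2 and 3 could also look like reactogenicity falling with repeat dosing.

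Solicited reactogenicity after each vaccination, by formulation against saline, is the first primary safety measure listed in protocol 3.2.1. SAP 1 says tolerability and safety will inform later development decisions.

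**Working it through.** **Inputs.** From the documents: 12 subjects per group (protocol summary; SAP 2.2), percentage = 100 x n/N with N the group total (SAP 5.1), and the Safety Population requiring one dose only (SAP 5.3). The documents give neither an expected number of missed doses nor a per-dose reaction rate, and there is no planned figure to reproduce. I therefore assume m = 0 to 4 subjects per group not given a particular dose, and rates among those dosed of 25%, 50% and 75%.

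**Formula.** Let r be the rate among those who received the dose.

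- Reactors: n = r x (12 - m)
- Percentage under the general rule: n/12 = r x (12 - m)/12
- Percentage over those dosed: n/(12 - m) = r
- Shortfall: r x m/12

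**Results.** Printed percentage, with the shortfall in points in brackets:

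| m | r = 25% | r = 50% | r = 75% |
|---|---|---|---|
| 0 | 25.0 (0) | 50.0 (0) | 75.0 (0) |
| 1 | 22.9 (2.1) | 45.8 (4.2) | 68.75 (6.25) |
| 2 | 20.8 (4.2) | 41.7 (8.3) | 62.5 (12.5) |
| 3 | 18.75 (6.25) | 37.5 (12.5) | 56.25 (18.75) |
| 4 | 16.7 (8.3) | 33.3 (16.7) | 50.0 (25.0) |

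Each missed dose removes one twelfth (8.3%) of the rate among those dosed.

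**Excess over saline.** Assume 60% among those dosed on a formulation, 40% on saline, and doses missed only on the formulation. With m = 2 the formulation prints 0.60 x 10/12 = 50%, and the excess falls from 20 points to 10. With m = 3 it prints 0.60 x 9/12 = 45%, and the excess falls to 5 points.

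**Order of two groups.** Suppose one group has three doses not given and 5 of the 9 dosed subjects react (5/9 = 55.6%). Another is fully dosed and 6 of 12 react (50.0%). Over 12, the first group prints 5/12 = 41.7%, so it appears the milder of the two.

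**Where the effect stops.** Everyone in the Safety Population has received dose 1, so that table is unaffected. For all vaccinations combined, the question is whether a subject reacted at all, and the full Safety Population is the proper denominator. The Fisher tests in SAP 5.7.4.1 and 5.7.5.1 concern at least one injection-site event and the frequency of events by coded term. They are not specified by dose.

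**The case against.** The strongest reply is that the SAP does not actually state a denominator of 12 for doses 2 and 3. The sentence naming the Safety Population concerns tabulation by severity. The dose-by-dose sentence speaks of a number of subjects and names neither a population nor a percentage, and a count cannot be diluted. SAP 5.1 also refers to the population size relevant to the table, which leaves some room for a dose-specific N. The table shells are a separate document (SAP 10) and might supply one. This stands as a limit: the denominator follows from the general rules and is not written in the sentence itself. But those rules are the only ones the SAP gives, and they lead to the group total.

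A reader might infer that a subject denied a later dose is recorded as reaction-free. The documents do not support that. The earlier reaction still appears under its own dose, in the combined summary and in the listings. The subject shows no event only in the summary for the dose not received.

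A reader might also infer that the most reactogenic formulation will look milder. That depends on doses being missed unequally, and nothing in the documents says how often this will happen. Doses are 56 days apart, and the Phase 1 reactions in protocol 2.1.6 were mainly mild to moderate. Under protocol 5.3.3, confounding symptoms may lead first to postponement. Three participants with the same related Grade 3 clinical event would meet a halting rule in protocol 9.5, so some of the three-dose examples would not arise undisturbed. One or two withheld doses could still occur without a halt.

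The SAP 5.7.5.1 sentence about the respective vaccination is ambiguous: it may mean vaccine group and not dose. It does not by itself establish dose-by-dose adverse event tables.

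Finally, SAP 5.6 already plans a summary of doses administered and a listing with a comment where a dose was not given. A reader could rebuild the denominators from these. That reduces the harm, but a summary of a primary safety outcome should not need rebuilding.

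**Conclusion.** The point holds in a conditional form. The plan's general rules produce a percentage for dose 2 or 3 that is too low, as a rate among those exposed, whenever someone in the group misses that dose and anyone dosed reacts. The factor is (12 - m)/12. Over the assumed range of one to four missed doses and rates of 25% to 75%, the shortfall is 2.1 to 25.0 points. With no missed doses it is zero. The direction is certain; the size cannot be known from the documents.

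A formulation with more withheld doses can therefore look milder in the descriptive dose 2 and 3 summaries. The stronger conclusion, that the safety comparison with saline as a whole is biased, is not supported, because the formal tests and the combined summary do not use dose-specific percentages. The verdict assumes that percentages accompany the dose-by-dose counts and that the table shells, not available here, follow SAP 5.1 as written.

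**What to change.** In SAP 5.7.5.2, state that N for each dose-specific table and bar chart is the Safety Population subjects who received that dose, and print that N by group. Apply the same rule in SAP 5.7.5.1 if adverse event tables are produced by dose, and clear up the wording there. Keep the full Safety Population for all vaccinations combined.

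Beside the dose 2 and 3 tables, show the number of doses not given, by group and reason. The SAP 5.6 summary and listing already supply the source. This display is needed because the new denominator removes the dilution but not the selection: subjects who receive later doses include those who tolerated the earlier ones, so an apparent fall with repeat dosing may persist.

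The cost is SAP wording and table headers, with no new data and no change to conduct. Denominators for doses 2 and 3 become slightly smaller if doses are missed, and the dose-specific comparison is then among those dosed and no longer among all randomized.

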#### **5.7.5.3 CHHI Reactogenicity**

All subjects will be observed for at least 60 minutes after application of the *N. americanus* larvae during CHHI to detect and treat any immediate AEs. Subjects will also complete study memory aids after CHHI beginning with the day of larval application and through Day 280 when they will be treated with albendazole to cure their infections. For the first 4 weeks after application of the *N. americanus* Larval Inoculum, the memory aids will be used to record pruritus, pain, tenderness, rash and swelling at the site of larval application, as well as cough and sore throat (to capture symptoms that may possibly be related to larval migration through the lungs). Starting on Day 175 (approximately 4 weeks after CHHI) of the study until the subject receives their first dose of albendazole, the memory aids will be used to record nausea, vomiting, diarrhea, abdominal pain, abdominal bloating and flatulence. CHHI reactogenicity events are AEs that are known to occur with hookworm infection.

Solicited and Unsolicited events post-CHHI will be summarized by frequency counts and percentages will be tabulated by severity to Vaccine Group using the Per-protocol Population.

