### 2.1.9.1 Experience with CHHI at George Washington University

A Phase 1 clinical trial of CHHI is currently underway at George Washington University (GWU) in Washington, DC, the same study site as will be used for the study described in this clinical protocol. This feasibility study (NCT01940757) is being conducted by [name] serving as study Principal Investigator. In it, 20 volunteers between the ages of 18 and 45 years who have no history of infection or exposure to hookworm were enrolled into 2 cohorts in a staggered fashion. In the first cohort volunteers received 25 *N. americanus* larvae whereas in the second cohort they received 50 larvae. All subjects (except 2 who were enrolled into a donor sub-study, see below) were cured of their infections by administering albendazole between 12 and 18 weeks post-infection.

In this study, adverse events have been mostly related to papulovesicular rash and pruritus at the site of larval application on the skin, and mild-to-moderate gastrointestinal symptoms most likely related to development of adult hookworms in the gastrointestinal tract. The skin reactions occurred immediately after application of larvae, have been graded by the study subjects as mild or moderate in most cases, and these have in some cases lasted for up to one month, sometimes with residual hyperpigmentation that gradually fades over time. Gastrointestinal symptoms consisting principally of mild to moderate abdominal bloating, flatulence and episodic nausea begin to occur approximately 4-6 weeks after infection. Skin reactions were more common in the 50 L3 cohort compared to the 25 L3 cohort, although there were no significant differences between the cohorts in incidence or severity of gastrointestinal complaints.

In the first cohort (25 L3), 3 of 10 subjects developed hookworm infections with eggs detectable in fecal samples by microscopy and PCR, whereas in the second (50 L3) cohort, 9 of 10 did. Mean egg counts, as estimated by the McMaster Method using all collected fecal samples, varied from 0 to 33 eggs per gram (epg) of feces in the 25 L3 cohort and from 0 to 133 epg in the 50 L3 cohort. Given the high rate of infection in the 50 L3 cohort, this will be the dose used in the Phase 2 clinical trial described in this protocol.

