3. Collect prior week's weekly GI symptom memory aid and give new weekly GI symptom memory aid.
4. Obtain fecal sample for parasitological testing.

Study Day 189 (Visit #21)

1. Perform basic history and physical exam, emphasizing examination of any acute complaints.
2. Record vital signs.
3. Obtain fecal sample for parasitological testing.
4. Collect prior week's weekly GI symptom memory aid and give new weekly GI symptom memory aid.
5. Obtain blood for hematology, antibody and cellular assays.

Study Day 196 (Visit #22) – Telephone Call

1. Review interim medical history emphasizing any acute signs or symptoms (including entries on the GI symptom memory aid).
2. Collect concomitant medication information.

Study Day 203 (Visit #23)

1. Perform basic history and physical exam, emphasizing examination of any acute complaints.
2. Record vital signs.
3. Obtain fecal sample for parasitological testing.
4. Collect prior week's weekly GI symptom memory aid and give new weekly GI symptom memory aid.
5. Obtain blood for hematology.

Study Day 210 (Visit #24) - Telephone Call

1. Review interim medical history emphasizing any acute signs or symptoms (including entries on the GI symptom memory aid).
2. Collect concomitant medication information.

Study Day 217 (Visit #25)

1. Perform basic history and physical exam, emphasizing examination of any acute complaints.
2. Record vital signs.
3. Obtain fecal sample for parasitological testing.
4. Collect prior weeks' GI symptom memory aids and give two new weekly GI symptom memory aids.
5. Obtain blood for hematology.

Study Day 224 (Visit #26) - Telephone Call

1. Review interim medical history emphasizing any acute signs or symptoms (including entries on the GI symptom memory aid).
2. Collect concomitant medication information.

Study Day 231 (Visit #27)

1. Perform basic history and physical exam, emphasizing examination of any acute complaints.
2. Record vital signs.
3. Obtain fecal sample for parasitological testing.
4. Collect prior weeks' GI symptom memory aids and give two new weekly GI symptom memory aids.

5. Obtain blood for hematology, antibody and cellular assays.

Study Day 238 (Visit #28) - Telephone Call

1. Review interim medical history emphasizing any acute signs or symptoms (including entries on the GI symptom memory aid).
2. Collect concomitant medication information.

Study Day 245 (Visit #29)

1. Perform basic history and physical exam, emphasizing examination of any acute complaints.

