### 9.2.3 CHHI Reactogenicity

All subjects will be observed for at least 60 minutes after application of the *N. americanus* larvae during CHHI to detect and treat any immediate AEs. Subjects will also complete study memory aids after CHHI beginning with the day of larval application and through Day 280 when they will be treated with albendazole to cure their infections. For the first 4 weeks after application of the *N. americanus* Larval Inoculum, the memory aids will be used to record pruritus, pain, tenderness, rash and swelling at the site of larval application, as well as cough and sore throat (to capture symptoms that may possibly be related to larval migration through the lungs). Starting on Day 175 (approximately 5 weeks after CHHI) of the study until the participant receives their first dose of albendazole, the memory aids will be used to record nausea, vomiting, diarrhea, abdominal pain, abdominal bloating and flatulence. Female participants of childbearing potential will additionally capture on the memory aids the form of contraception they are using. The memory aids will include a printed reminder of the potential risks associated with use of albendazole during pregnancy.

Subjects will also be asked to record any medications taken and any emergency room or healthcare provider visits (other than routine check-ups) through Day 297. The subject memory aid will be reviewed with the subject at subsequent clinic visits.

CHHI reactogenicity events are AEs that are known to occur with hookworm infection. The following Toxicity Grading Scales will be used to grade solicited local (larval application site) and systemic (subjective and quantitative) reactions:

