### **5.2 Definition**

**Baseline:** Baseline is defined as the latest non-missing assessment (whether from scheduled or unscheduled) prior to the first dose administration of the study vaccine, unless otherwise stated.

The **Post-baseline** values are defined as measurements taken after the first administration of study product.

**Change from Baseline:** The change from baseline values will be calculated as post baseline value minus the baseline value.

**An Adverse Event** is any untoward medical occurrence in a subject or clinical investigation in a subject administered a pharmaceutical product and which does not necessarily have to have a causal relationship with this vaccination. An adverse event can be any unfavorable sign (including an abnormal laboratory finding), symptom, or disease temporally associated with the use of the investigational product, whether considered related or not related to the investigational product.

A pre-vaccination condition is any event in a clinical study subject that occurs after he/she signed the Informed Consent Form (ICF) up until the first administration of study vaccine. All pre-vaccination conditions will be considered as medical history whereas any pre-vaccination condition that worsens after vaccination will be considered as an AE.

**An SAE** is any AE that results in death, is life-threatening (this refers to an event in which the subject was at risk of death at the time of the event; it does not refer to an event that hypothetically might have caused death had it been more severe), requires inpatient hospitalization or prolongation of existing hospitalization, results in persistent or significant disability/incapacity, is a congenital anomaly/birth defect, requires medical or surgical intervention to prevent any of the occurrences noted above.

**Unexpected Adverse Event:** Any adverse event, the specificity or severity of which is not consistent with the current Investigator's Brochure.

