#### 5.7.5 Safety Analysis

All safety assessments, including adverse events, solicited and unsolicited adverse events during the post-vaccination phase and post-CHHI phase, clinical laboratory test results, vital signs, (blood pressure [mmHg], heart rate [bpm], and oral temperature [Degrees Celsius]), abnormal physical examination

findings will be listed by subject and tabulated when applicable. The analysis will be performed on the Safety Population.

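### The SAP contradicts itself on the population for post-challenge safety, and its dedicated CHHI table leaves out challenged subjects who do not complete the study

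*SAP*

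**What the plan says.** **Outcome.** Protocol 3.2.1 and SAP 4.1 list as primary safety outcomes the solicited events from the day of CHHI (Day 140) to Day 280, and the unsolicited events from CHHI to Day 297.

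**Population.** SAP 5.3 says of the Safety Population: "This population will be used to summarize safety variables and will summarize subjects as vaccinated". SAP 5.7.5 lists solicited and unsolicited events of both the post-vaccination and the post-CHHI phase, then states: "The analysis will be performed on the Safety Population". The post-vaccination table in 5.7.5.2 follows this rule. The CHHI table in 5.7.5.3 does not: its events "will be tabulated by severity to Vaccine Group using the Per-protocol Population". SAP 5.3 restricts that set to randomized subjects who "received all three study vaccinations and CHHI and completed the study without any major protocol deviations", or who completed with deviations that the Investigator judges to have no significant impact. No population of all challenged subjects is defined.

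**Withdrawal.** Protocol 7.7 provides for subjects who withdraw before Day 280, whether for adverse events or personal reasons.

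**Diary.** Protocol 9.2.3 has GI symptoms recorded until the first albendazole dose, "Starting on Day 175 (approximately 5 weeks after CHHI) of the study". SAP 5.7.5.3 gives the same day but calls it about 4 weeks. Protocol 2.1.9.1 reports that GI symptoms "begin to occur approximately 4-6 weeks after infection". At Days 189 and 203, Protocol 7.3 tells staff to "give new weekly GI symptom memory aid" (one form), although the next clinic visit is two weeks later.

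**The concern.** The table that reports a primary safety outcome selects subjects on something that happens after the challenge: staying to the end. Leaving because of challenge symptoms is a route out that the protocol itself foresees. If symptomatic subjects are the ones who leave, the table understates how the challenge was tolerated. If vaccination changes symptoms, the understatement could differ between arms. A programmer given both instructions would probably follow the specific one in 5.7.5.3. Missing diary weeks would add a second loss in the same outcome, because an unsolicited week can be read as a symptom-free one.

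**Working it through.** **1. Which instruction governs.** SAP 5.3 and 5.7.5 give a general rule that names post-CHHI events. SAP 5.7.5.3 gives a specific rule for the same events with a different population. Both cannot be followed. The SAP's section on changes from the protocol (section 7) does not mention the restriction, and 5.7.5.2 uses the Safety Population, so the restriction is not explained as a choice.

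**2. Who drops out of the CHHI table.** Under SAP 5.3:
- challenged subjects who withdraw before completing the study;
- any subject challenged after a missed dose, if that occurs;
- completers with a major deviation that the Investigator does not judge to be without significant impact.

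**3. Whether the other tables make up for it.** The tables in SAP 5.7.5.1 run from first dose to the last study procedure on the Safety Population, so leavers are counted. No post-CHHI period is separated out. A subject counts once per preferred term, at highest severity. Nausea and vomiting are solicited in both phases (Protocol 9.1), so a post-challenge rate cannot be read off these tables. Their denominator also includes anyone vaccinated but never challenged.

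**4. Size (illustration).** Input: 12 per arm (SAP 3.1), all challenged. Assumptions: x subjects have a severe GI event and k of those x leave. All challenged = x/12; Per Protocol = (x − k)/(12 − k). Exact (Clopper-Pearson) 95% intervals are in brackets.

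| x | k | All challenged | Per Protocol |
|---|---|---|---|
| 1 | 1 | 1/12 = 8.3% (0.2 to 38.5) | 0/11 = 0% (0 to 28.5) |
| 2 | 1 | 2/12 = 16.7% (2.1 to 48.4) | 1/11 = 9.1% (0.2 to 41.3) |
| 2 | 2 | 2/12 = 16.7% (2.1 to 48.4) | 0/10 = 0% (0 to 30.8) |
| 3 | 2 | 3/12 = 25.0% (5.5 to 57.2) | 1/10 = 10.0% (0.3 to 44.5) |

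The direction depends on who leaves. If two subjects without events leave and both cases stay, Per Protocol gives 2/10 = 20.0% against 2/12 = 16.7%.

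**5. Day 175 label.** (175 − 140)/7 = 5.0 weeks. The protocol's figure reproduces; the SAP's 4 weeks does not.

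**6. Diary count.** Needed from Day 175 to Day 280: (280 − 175)/7 = 15 weekly forms. Issued under Protocol 7.3:
- one each on Days 175, 182, 189 and 203: 4
- two each on Days 217, 231, 245 and 259: 8
- one on Day 273: 1

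The total is 4 + 8 + 1 = 13. At seven days per form from issue, Days 196 to 202 and 210 to 216 have none.

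**7. The week before.** Two weekly forms given on Day 154 run to Day 154 + 14 = Day 168. The GI form starts on Day 175. Days 168 to 174 therefore have no diary, yet weeks 4 to 6 after challenge are Days 168 to 182.

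**The case against.** **Leavers are not lost to safety reporting.** A reader might infer that subjects who leave disappear altogether. The documents do not support that. All adverse events are listed, and the whole-study tables of adverse events, serious events and events of special interest use the Safety Population. GI bleeding, anemia above Grade 1 and pneumonitis are events of special interest after CHHI (Protocol 9.3.4). The overview table also counts subjects with an event leading to discontinuation. This stands: the loss is confined to the dedicated CHHI table. It does not remove the contradiction, for the reasons in step 3 of the working.

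**Early treatment is not an exclusion.** A reader might add subjects given albendazole early. SAP 5.3 does not list that, and an early-treated subject can still complete follow-up. This stands.

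**The bias is not demonstrated.** Protocol 2.1.9 describes experimental infections as well tolerated overall, and the earlier study at this site saw mild-to-moderate GI symptoms. Neither section reports attrition of the kind assumed above. This stands as to size.

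**The diary gaps may be a drafting slip.** Day 217 collects forms in the plural although Day 203 gives one, and the telephone calls on Days 196 and 210 review entries. That is a fair reading, but no further form is described at those calls. Days 168 to 174 follow the diary design in Protocol 9.2.3, and unsolicited events are still collected then. It is therefore not right to count that week as a third contradiction.

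**Laboratory baseline.** A reader might call it an error that change after CHHI is measured from a value "prior to the first dose administration of the study vaccine, unless otherwise stated". It is not: laboratory adverse events are graded on absolute thresholds (Protocol Table 5), results are summarized by visit, and all arms follow one blood-draw schedule.

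**Conclusion.** The contradiction between SAP 5.3 and 5.7.5 on one side and 5.7.5.3 on the other is real, and it concerns a primary outcome. As written, the specific instruction conditions the CHHI table on study completion. At 12 per arm, one symptomatic leaver turns 8.3% into 0%, and two turn 16.7% into 0%. The numbers of leavers are assumed. Rates that are too low are likely if leavers are symptomatic, but neither the size nor a difference between arms can be stated from the documents.

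The diary shortfall is secondary: 2 of the 15 weeks in the stated GI window (13%), if Protocol 7.3 is followed literally. Days 168 to 174 are a limit of the design, to be stated rather than corrected as an inconsistency. The laboratory baseline is an optional addition.

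**What to change.** **SAP 5.3 and 5.7.5.3 (needed, before unblinding).** Define a Challenged Population: all subjects who received the larval inoculum, grouped by vaccine or placebo actually received. Use it for the post-CHHI solicited and unsolicited tables, and align 5.7.5 with it. Keep Per Protocol at most as supportive. Moving to the full Safety Population would also end the contradiction, but it would put never-challenged subjects in the denominator.

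**Diary (secondary).** Reconcile Protocol 7.3 with 9.2.3 by issuing two weekly GI forms at Days 189 and 203. Correct the SAP's label for Day 175 to 5 weeks. State in the report that no diary covers Days 168 to 174. If the visits have passed, show uncovered weeks as not solicited, not as symptom-free.

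**Laboratory (optional).** Add change from the Day 140 pre-inoculation value for the CHHI phase. Appendix A schedules 604 mL of blood by Day 126, so change from before dose 1 mixes blood draws with the challenge.

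**Cost.** SAP wording, one population flag and two extra diary sheets per subject. Reported post-challenge rates may be higher than under Per Protocol.
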